5.6.5.4 DOSE DISCONTINUATION OF NIVOLUMAB

Treatment should be permanently discontinued for the following:

- Any Grade 2 drug-related uveitis or eye pain or blurred vision that does not respond to topical therapy and does not improve to Grade 1 severity within the re-treatment period OR requires systemic treatment.
- Any Grade 3 non-skin, drug-related adverse event lasting > 7 days, with the following exceptions for drug-related laboratory abnormalities, uveitis, pneumonitis, bronchospasm, neurologic toxicity, hypersensitivity reactions, and infusion reactions:
 - Grade 3 drug-related uveitis, pneumonitis, bronchospasm, neurologic toxicity, hypersensitivity reaction, or infusion reaction of any duration requires discontinuation.
 - Grade 3 drug-related laboratory abnormalities do not require treatment discontinuation except:
 - Grade 3 drug-related thrombocytopenia > 7 days or associated with bleeding requires discontinuation
 - Any drug-related liver function test (LFT) abnormality that meets the following criteria require discontinuation:
 - AST or ALT > 8 x ULN
 - Total bilirubin > 5 x ULN
 - Concurrent AST or ALT > 3 x ULN and total bilirubin > 2 x ULN
- Any Grade 4 drug-related adverse event or laboratory abnormality, except for the following events which do not require discontinuation:
 - Isolated Grade 4 amylase or lipase abnormalities that are not associated with symptoms or clinical manifestations of pancreatitis and decrease to < Grade 4 within 1 week of onset.
 - Isolated Grade 4 electrolyte imbalances/abnormalities that are not associated with clinical sequelae and are corrected with supplementation/appropriate management within 72 hours of their onset.
- Any dosing delay lasting > 8 weeks with the following exceptions:
 - Dosing delays to allow for prolonged steroid tapers to manage drug-related adverse events are allowed. Prior to re-initiating treatment in a subject with a dosing delay lasting > 8 weeks, the PI must be consulted. Tumor assessments should continue as per protocol even if dosing is delayed.
 - Dosing delays > 8 weeks that occur for non-drug-related reasons may be allowed if approved by the PI. Prior to re-initiating treatment in a subject with a dosing delay lasting > 8 weeks, the PI must be consulted. Tumor assessments should continue as per protocol even if dosing is delayed.
- Any adverse event, laboratory abnormality, or intercurrent illness, which, in the judgment of the Investigator, presents a substantial clinical risk to the subject with continued Nivolumab dosing.

5.6.6 MANAGEMENT OF INFUSION REACTIONS:

Since Nivolumab contains only human immunoglobulin protein sequences, it is unlikely to be immunogenic and induce infusion or hypersensitivity reactions. However, if such a reaction were to occur, it might manifest with fever, chills, rigors, headache, rash, pruritus, arthralgias, hypo or hypertension, bronchospasm, or other symptoms. All Grade 3 or 4 infusion reactions should be reported within 24 hours to University of Cincinnati PI (coordinating center), as well as to the local PI and reported as an SAE if criteria are met. Infusion reactions should be graded according to NCI CTCAE (version 5.0) guidelines.

Treatment recommendations are provided below and may be modified based on local treatment standards and guidelines as appropriate:

For Grade 1 symptoms: (Mild reaction; infusion interruption not indicated; intervention not indicated)

Remain at bedside and monitor subject until recovery from symptoms. The following prophylactic premedications are recommended for future infusions: diphenhydramine 50 mg (or equivalent) and/or acetaminophen 325 to 1000 mg at least 30 minutes before additional Nivolumab administrations.

For Grade 2 symptoms: (Moderate reaction requires therapy or infusion interruption but responds promptly to symptomatic treatment [e.g., antihistamines, non-steroidal anti-inflammatory drugs, narcotics, corticosteroids, bronchodilators, IV fluids]; prophylactic medications indicated for ≤ 24 hours).

Stop the Nivolumab infusion, begin an IV infusion of normal saline, and treat the subject with diphenhydramine 50 mg IV (or equivalent) and/or acetaminophen 325 to 1000 mg; remain at bedside and monitor subject until resolution of symptoms. Corticosteroid or bronchodilator therapy may also be administered as appropriate. If the infusion is interrupted, then restart the infusion at 50% of the original infusion rate when symptoms resolve; if no further complications ensue after 30 minutes, the rate may be increased to 100% of the original infusion rate. Monitor subject closely. If symptoms recur then no further Nivolumab will be administered at that visit. Administer diphenhydramine 50 mg IV, and remain at bedside and monitor the subject until resolution of symptoms. The amount of study drug infused must be recorded on the electronic case report form (eCRF). The following prophylactic premedications are recommended for future infusions: diphenhydramine 50 mg (or equivalent) and/or acetaminophen 325 to 1000 mg should be administered at least 30 minutes before additional Nivolumab administrations. If necessary, corticosteroids (recommended dose: up to 25 mg of IV hydrocortisone or equivalent) may be used.

For Grade 3 or Grade 4 symptoms: (Severe reaction, Grade 3: prolonged [i.e., not rapidly responsive to symptomatic medication and/or brief interruption of infusion]; recurrence of symptoms following initial improvement; hospitalization indicated for other clinical sequelae [e.g., renal impairment, pulmonary infiltrates]). Grade 4: (life threatening; pressor or ventilator support indicated).

Immediately discontinue infusion of Nivolumab. Begin an IV infusion of normal saline, and treat the

subject as follows. Recommend bronchodilators, epinephrine 0.2 to 1 mg of a 1:1,000 solution for subcutaneous administration or 0.1 to 0.25 mg of a 1:10,000 solution injected slowly for IV administration, and/or diphenhydramine 50 mg IV with methylprednisolone 100 mg IV (or equivalent), as needed. Subject should be monitored until the investigator is comfortable that the symptoms will not recur. Nivolumab will be permanently discontinued. Investigators should follow their institutional guidelines for the treatment of anaphylaxis. Remain at bedside and monitor subject until recovery from symptoms. In the case of late-occurring hypersensitivity symptoms (e.g., appearance of a localized or generalized pruritus within 1 week after treatment), symptomatic treatment may be given (e.g., oral antihistamine, or corticosteroids).

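### When infusion-reaction symptoms recur after restart, Section 5.6.6 can be read as allowing later nivolumab doses or as requiring a permanent stop

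*Combined protocol and SAP*

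**What the plan says.** Section 5.6.6 describes Grade 2 as follows: "Moderate reaction requires therapy or infusion interruption but responds promptly to symptomatic treatment". For that grade the infusion is stopped and symptoms are treated. Then: "If the infusion is interrupted, then restart the infusion at 50% of the original infusion rate when symptoms resolve". The paragraph foresees that the restart may fail: "If symptoms recur then no further Nivolumab will be administered at that visit". It ends with advice on later doses: "The following prophylactic premedications are recommended for future infusions: diphenhydramine 50 mg (or equivalent) and/or acetaminophen 325 to 1000 mg should be administered" before further nivolumab.

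The next paragraph covers Grades 3 and 4. Its Grade 3 description lists, among other features, "recurrence of symptoms following initial improvement; hospitalization indicated for other clinical sequelae". For these grades the infusion stops at once and "Nivolumab will be permanently discontinued".

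Section 5.6.5.4 has its own stopping rule: "Grade 3 drug-related uveitis, pneumonitis, bronchospasm, neurologic toxicity, hypersensitivity reaction, or infusion reaction of any duration requires discontinuation".

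Four other provisions bear on the point:
- The opening of Section 5.6.6 requires CTCAE v5.0 grading of infusion reactions, and a report of Grade 3 or 4 reactions to the coordinating-center PI within 24 hours.
- The same opening presents the treatment steps as recommendations that sites may adapt to local standards.
- Section 8.8 requires every change of grade within an episode to be recorded.
- Section 9.2 makes Grade 3 and 4 adverse events a dichotomous secondary endpoint, expected at 13%, with an exact 95% interval.

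**The concern.** A reaction that settles, allows a restart and then returns is foreseen in the Grade 2 paragraph and also fits the Grade 3 description. The first limits the stop to the current visit. The second ends treatment. A clinician who follows the Grade 2 paragraph to its end is never told that the recurrence may have changed the grade.

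The main stake is patient safety: whether a patient with a recurrent acute reaction may be exposed again at the next cycle. The 24-hour report is a second stake, because a reaction left at Grade 2 does not trigger it under Section 5.6.6. A lesser one is the count of patients with a Grade 3-4 event.

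**Working it through.** **Text comparison.** Take one patient whose infusion is interrupted for a moderate reaction, whose symptoms resolve, and whose symptoms return after the restart.

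| Step | Grade 2 branch, 5.6.6 | Grade 3 branch, 5.6.6, and 5.6.5.4 |
|---|---|---|
| Does the text describe this event? | Yes: recurrence after restart is named | Yes: recurrence after initial improvement is named |
| Action at this visit | No more drug | Infusion stopped at once |
| Later doses | Not ruled out; premedication for future infusions follows | Permanently discontinued |
| 24-hour report to the coordinating-center PI | Not triggered by grade | Triggered |

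1. The Grade 2 branch restarts only after symptoms resolve. Symptoms that have resolved have also improved, so their return is a recurrence after improvement. The two descriptions overlap.
2. The action at the visit is compatible, since both branches stop the drug. The conflict concerns later doses.
3. No sentence in 5.6.6 moves the patient from the Grade 2 branch to the Grade 3 branch, and none says which prevails.
4. The latitude for local adaptation belongs to the treatment steps in 5.6.6. The rule in 5.6.5.4 carries no such allowance, so the latitude does not resolve the conflict.

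**Size of the endpoint effect.** Inputs: 35 patients (Synopsis, Sample Size Justification), 10% drop-out and 39 enrolled (Synopsis and Section 9.3), 13% expected (Section 9.2).

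- Enrolled total: 35 / (1 - 0.10) = 38.9, rounded up to 39. This reproduces the plan's figure.
- Expected count: 0.13 × 39 = 5.07, about 5 patients.
- One patient moved: 1/39 = 2.6 percentage points, or 1/35 = 2.9 points if only 35 are analysed.

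Exact (Clopper-Pearson) 95% intervals:

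| n | Count | Rate | 95% CI |
|---|---|---|---|
| 39 | 5 | 12.8% | 4.3 to 27.4 |
| 39 | 6 | 15.4% | 5.9 to 30.5 |
| 35 | 5 | 14.3% | 4.8 to 30.3 |
| 35 | 6 | 17.1% | 6.6 to 33.6 |

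The intervals with and without the extra patient overlap almost completely.

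**The case against.** The best reply is that the protocol, read in sequence, already gives one route. The reaction starts at Grade 2 and recurs. It is re-graded under CTCAE v5.0, the change is recorded under Section 8.8, and the stopping rule in 5.6.5.4 then applies, with no exception for a reaction that began at Grade 2. On this view only a cross-reference is missing.

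Much of this stands for the recorded grade. The endpoint and the 24-hour report follow the grade, not the management step, so a careful site would probably record Grade 3. It does not settle dosing. The Grade 2 paragraph gives its own instruction for the same event and limits it to one visit, a limit that says little if treatment was meant to end.

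A reader might infer that the protocol orders these patients to be dosed again and also stopped. The text does not go that far. It withholds drug at the visit and leaves later doses open. The premedication sentence closes the whole paragraph and serves every Grade 2 reaction, including those that never recur. A permanent stop would not breach the Grade 2 wording.

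It is also fair to say that the Grade 3 description does not mention a restart. That leaves room to argue that a different event was meant, but the protocol does not say so, and the ambiguity remains.

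**Conclusion.** The inconsistency is real and sits in the current text. Symptoms that recur after restart fall under one passage that leaves later nivolumab open and two that require permanent discontinuation, and the protocol does not say when the Grade 2 branch is left. The conflict matters chiefly for patient safety and for reporting, and it should be corrected.

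The conclusion assumes that the features in the Grade 3 description are alternatives, as their separation by semicolons suggests, and that the reaction is drug-related, as 5.6.5.4 requires. The documents refer to CTCAE v5.0 without reproducing its infusion-reaction wording, so the comparison rests on the descriptions printed in 5.6.6.

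A reader might go on to infer that the Grade 3-4 rate is materially unreliable. The documents do not support that. The shift of 2.6 points per patient (2.9 at n = 35) arises only if a site leaves the event at Grade 2 despite the grading and recording rules, and only if that patient has no other Grade 3-4 event. No frequency is given, and Section 5.6.6 regards such reactions as unlikely. The 13% is an expectation: Sections 9.5.2 and 9.6.2 point to hypotheses in Section 9.3, but that section states hypotheses for DFS only, so no safety threshold is set that one patient could cross. The primary DFS design is unaffected.

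**What to change.** The sponsor and clinicians should reconcile the Grade 2 recurrence instruction in Section 5.6.6 with the Grade 3 description and action in the same section and with the stopping rule in Section 5.6.5.4. One instruction should then apply to symptoms that recur after restart. It should state when the patient leaves the Grade 2 branch, and cross-refer to the grade definition and the 24-hour reporting rule. Which clinical rule applies is for them to decide.

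A separate sentence fixing the grade of this event is not advised. CTCAE grading and the recording of grade changes are already required, and fixing the event at Grade 3 would, through 5.6.5.4 as written, choose the dosing rule indirectly.

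The cost is one or two sentences in a protocol amendment. No extra patients or data are needed, and no design figure changes.

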5.7 USE IN PREGNANCY

If, following initiation of the study drug, it is subsequently discovered that a study subject is pregnant or may have been pregnant at the time of study exposure, including during at least 5 half-lives after product administration, the investigator must immediately notify the University of Cincinnati PI and BMS of this event and complete and forward a Pregnancy Surveillance Form to BMS within 24 hours and in accordance with SAE reporting procedures described in Section 8.

In most cases, the study drug will be permanently discontinued in an appropriate manner (e.g., dose tapering if necessary for subject safety).

In the rare event that the benefit of continuing study drug is thought to outweigh the risk, after consultation with BMS and the University of Cincinnati PI, the pregnant subject may continue study drug, after a thorough discussion of benefits and risk with the subject.

Protocol required procedures for study discontinuation and follow-up must be performed on the subject unless contraindicated by pregnancy (e.g., x-ray studies). Other appropriate pregnancy follow-up procedures should be considered if indicated.

Follow-up information regarding the course of the pregnancy, including perinatal and neonatal outcome and where applicable, offspring information must be reported on the Pregnancy Surveillance form.

Any pregnancy that occurs in a female partner of a male study participant should be reported to BMS and the University of Cincinnati PI. Information on this pregnancy will be collected on the Pregnancy Surveillance Form.

5.7.1 USE IN NURSING WOMEN

It is unknown whether Nivolumab is excreted in human milk. Since many drugs are excreted in human milk, and because of the potential for serious adverse reactions in the nursing infant, subjects who are breast-feeding are not eligible for enrollment

6.0 STUDY FLOW CHART

Trial Period	Screening	Treatment							Post-Treatment/Follow-up ^q
		1	2	3	4	5	6		
Scheduling Window (Days)	-28 to -1	0 ^(j)	± 3	± 3	± 3	± 3	± 3	30 Days post-discon +/- 3 ^(l)	Every 12 weeks +/- 4 weeks
Adjuvant Treatment (Week)		1	5	9	13	17	21		
Informed Consent	X								
Inclusion/ Exclusion Criteria ^(R)	X								
Demographics and Medical History ^(m)	X								
Prior and Concomitant Medication Review	X	X	X	X	X	X	X	X	
Nivolumab Administration ^(a)		X	X	X	X	X	X		
Post-study anticancer therapy status								X	
Survival and Disease Status ^(k)									X
Review Adverse Events		X	X	X	X	X	X	X ⁽ⁱ⁾	
Full Physical Examination	X							X	
Directed Physical Examination		X	X	X	X	X	X		X ^(c)
Vital Signs and Weight	X ⁽ⁿ⁾	X	X	X	X	X	X	X	

Trial Period	Screening	Treatment							Post-Treatment/Follow-up ^q
		1	2	3	4	5	6		
Scheduling Window (Days)	-28 to -1	0 ^(j)	± 3	± 3	± 3	± 3	± 3	30 Days post-discon +/- 3 ^(l)	Every 12 weeks +/- 4 weeks
Adjuvant Treatment (Week)		1	5	9	13	17	21		
ECOG Performance Status ^(b)	X		X	X	X	X	X		
Pregnancy Test – Urine or Serum -HCG	X ^(p)								
CBC with Differential	X ^(o)	X ^(o)	X	X	X	X	X	X	
Comprehensive Serum Chemistry Panel ^(d)	X ^(o)	X ^(o)	X	X	X	X	X	X	
Urinalysis	X ^(o)	X ^(o)			X			X	
T3, FT4 and TSH	X ^(o)	X ^(o)			X			X	X ^(h)
PT/INR, PTT	X ^(o)								
Tumor Imaging ^(e)	X								X ^(e)
Archival Tissue Collection ^(f)	X							X ^(f)	
Correlative Studies Blood Collection ^(g)		X	X					X ^(g)	

a) Nivolumab will start 28-77 days after surgery. Start of cycle on Day 1 +/- 3 days.

b) ECOG to be done prior to treatment administration. For Day 1, must be done within 10 days but does not need to be repeated for Day 1 only.

c) Only required if assessing for disease recurrence.

- d) Magnesium, Phosphorous, LDH, uric acid should also be checked as part of CMP labs.
- e) PET/CT and CT neck with contrast preferred for screening. CT neck with contrast and CT chest or MRI neck and chest is also acceptable. Neck imaging must be completed pre-operatively but chest imaging may be pre or post-operatively. Follow-up tumor imaging will be at discretion of treating physician but is not required per protocol.
- f) Archival Resected tissue will be collected from pathology and sectioned per procedure manual. If biopsy or resection is performed per SOC at recurrence, tissue will also be collected at that time for analysis.
- g) On Day 1 and week 5, ensure correlative samples are collected prior to protocol treatment. A 3rd sample should be collected at the end of treatment visit. Correlatives will be placed in four 10ml lavender EDTA tubes.
- h) Thyroid function labs can be checked at physician's discretion on post treatment follow up.
- i) SAEs should be evaluated out to 100 days after drug discontinuation. All AEs should be followed until \leq Grade 1 or new therapy has begun. All non-serious AEs must be followed continuously for at least 30 days.
- j) Adjuvant treatment must be started 28-77 days after salvage surgery.
- k) May be assessed by phone or clinic visit
- l) Post discontinuation visit should occur at 30 days +/-3 days as above, or before new therapy begins, whichever occurs first.
- m) Medical History from last 10 years should be included
- n) Height also required only at screening
- o) Labs must be collected within 10 days of first treatment and within 72 hours prior to subsequent treatments. Screening labs can be used for Day 1 as long as within window.
- p) Must be collected within 72 hours of Day 1.
- q) Subjects who discontinue for reasons other than progressive disease will have post-treatment follow-up for disease status until disease progression, initiating a non-study cancer treatment, withdrawing consent or becoming lost to follow-up or the end of the study whichever occurs first. After documented disease progression each subject will be followed by telephone for overall survival until death, withdrawal of consent, or the end of the study, whichever occurs first.
- r) Protocol treatment must begin only after eligibility criteria are confirmed by the UC PI (registration)

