4.5 SUBJECT WITHDRAWAL/DISCONTINUATION CRITERIA

Subjects may withdraw consent at any time for any reason or be dropped from the trial at the discretion of the investigator. In addition, a subject may be withdrawn by the investigator if enrollment into the trial is inappropriate, the trial plan is violated, or for administrative and/or other safety reasons.

The End of Treatment and Follow-up visit procedures are listed in Section 6 (Protocol Flow Chart) and Section 7.9 (Visit Requirements). After the end of treatment, each subject will be followed for 30 days for adverse event monitoring (serious adverse events will be collected for 100 days after the end of treatment). Subjects who discontinue for reasons other than progressive disease will have post-treatment follow-up for disease status until disease progression, initiating a non-study cancer treatment, withdrawing consent or becoming lost to follow-up or the end of the study whichever occurs first. After documented disease progression each subject will be followed by telephone for overall survival until death, withdrawal of consent, or the end of the study, whichever occurs first.

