5.6.4.2 PROHIBITED CONCOMITANT MEDICATIONS

Subjects are prohibited from receiving the following therapies during the Screening and Treatment Phase of this trial:

- Biological therapy
- Immunotherapy not specified in this protocol
- Chemotherapy
- Investigational agents other than Nivolumab

- Live vaccines within 30 days prior to the first dose of trial treatment and while participating in the trial. Examples of live vaccines include, but are not limited to, the following: measles, mumps, rubella, varicella/zoster, yellow fever, rabies, BCG, and typhoid vaccine.
- Systemic glucocorticoids should be avoided if possible. Steroids are allowed as short bursts of 5-7 days if required for clinical indication (i.e. COPD) or to modulate symptoms from an event of clinical interest of suspected immunologic etiology. The chronic use of physiologic doses of corticosteroids may be approved after consultation with the Sponsor.

Subjects, who, in the assessment by the investigator, require the use of any of the aforementioned treatments for clinical management other than specified as allowed, should be removed from the trial. Subjects may receive other medications that the investigator deems to be medically necessary.

There are no prohibited therapies during the Post-Treatment Follow-up Phase.

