7.7.5 SURVIVAL FOLLOW-UP

Once a subject experiences confirmed disease relapse/progression or starts a new anti-cancer therapy, the subject moves into the survival follow-up phase and should be contacted by telephone or seen in clinic every 12 weeks +/- 4 weeks to assess for survival status until death, withdrawal of consent, or at the end of the study, whichever occurs first.

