9.3 SAMPLE SIZE

We expect that the use of the Nivolumab-based adjuvant therapy will improve 2 year disease-free survival (DFS) by 20%. The optimal single-arm two-stage design with time-to-event endpoints(Kwak & Jung, 2014) will be used to test the null hypothesis that DFS at 2 years $\leq 33\%$, which is based on the historic data, versus the alternative that DFS at 2 years $\geq 53\%$, by a one-sided, one-sample log-rank test with the power of 80% at a 5% significance level. After 17 patients are entered in the first stage, the trial will be terminated if the test statistic at stage 1 > 0.76 . If the trial goes on to the second stage, a total of 39 patients will be studied. We reject the null hypothesis if the test statistic at stage 2 > -1.62 . Considering a drop-out rate of 10%, a total of 39 patients are needed for this study.

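### Some sections stop relapse follow-up when non-study cancer therapy starts, others do not, and section 9 does not say how these patients enter the DFS analysis; relapses missed this way bias DFS upward

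*Combined protocol and SAP*

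**What the plan says.** **Sections with the stop.** For patients who discontinue for reasons other than progression, flow chart footnote q provides "post-treatment follow-up for disease status until disease progression, initiating a non-study cancer treatment, withdrawing consent or becoming lost to follow-up", and section 4.5 has the same rule. Section 7.4.3 moves any patient who starts new anti-cancer therapy into survival follow-up. Section 7.7.5 does the same: "Once a subject experiences confirmed disease relapse/progression or starts a new anti-cancer therapy, the subject moves into the survival follow-up phase". It lists confirmed relapse and new therapy as separate triggers, so the protocol foresees therapy without confirmed relapse.

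**Sections without the stop.** Section 7.5.8 follows every patient for relapse for 2 years in total. Section 7.7.4 monitors for relapse for up to 2 years and names only withdrawal of consent and death as earlier ends. The flow chart row for the 12-weekly contacts covers both survival and disease status.

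**Endpoint and analysis.** DFS (synopsis, 2.2, 9.1, 9.5.1) counts first evidence of any tumor, or death from any cause. New therapy is not an event. The only censoring statement is at end of study (synopsis, 9.1). The primary test is a "one-sided, one-sample log-rank test with the power of 80% at a 5% significance level".

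**Prohibited therapy during treatment.** Section 5.6.4.2 says that patients who need a prohibited treatment "for clinical management other than specified as allowed, should be removed from the trial". It does not say whether DFS follow-up continues for them. The efficacy set is everyone with at least one dose, and section 4.6 replaces nobody.

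**The concern.** A patient who starts other cancer treatment on suspicion of relapse is likely to be at high risk of relapse. If disease-status collection ends on that day and no relapse has been documented, a tumor found later is not recorded as a DFS event.

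The gap is plausible. Follow-up may be by phone when an outside oncologist sees the patient (7.7.4), only site investigators may determine recurrence (7.5.6), and biopsy is recommended rather than required (7.5.8).

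The primary test compares one arm with a fixed 2-year DFS of 33%. There is no control arm in which the same loss could cancel, so every relapse missed in this way moves the result toward a positive trial. Section 9 also leaves the analyst to choose, after the data are in, between censoring at therapy start and keeping the patient at risk to study end.

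**Working it through.** **1. Reproduce the design.** Inputs are from section 9.3 and the synopsis: null 33%, alternative 53%, stage 1 of 17, stage 1 limit 0.76, final limit 1.62 in absolute value, 35 patients before 10% dropout. Accrual is 3–4 per month (9.4). Exponential DFS is my assumption.

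- Hazards per year: λ0 = −ln(0.33)/2 = 0.554; λ1 = −ln(0.53)/2 = 0.317; ratio 0.573.
- Statistic: W = (O − E)/√E, with E = λ0 × total time at risk.
- Dropout: 35/0.90 = 38.9, so 39, as stated.
- Two-stage simulation at 3 per month, analysis 2 years after last entry, rejecting for W < −1.62: power 0.790, type I error about 0.040.

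This is close to the planned 80%. The nominal 5% is asymptotic, so about 4% is the baseline below. Two printing matters are separate from this point: the final inequality is printed in the opposite direction, and section 9.3 gives 39 where the synopsis gives 35 before dropout. I used the lower tail and 35.

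**2. Weight of one missed relapse.** Accrual takes 35/3 = 11.7 months = 0.972 years, so follow-up runs from 2 to 2.97 years. Under the null, mean survival over that span is (0.3300 − 0.1925)/(0.554 × 0.972) = 0.255. Expected events are 35 × (1 − 0.255) ≈ 26. One missed event with E unchanged moves W by 1/√26 ≈ 0.2. Missing 10% of them is 2.6 events, or about 0.5 on W.

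**3. Effect on type I error.** The documents give no share of relapses missed, so it is an assumed range. Setting: true 2-year DFS 33%, n = 35, 3 per month, all DFS events taken as relapses.

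| Relapses missed | Censored at therapy start | At risk to study end, later deaths counted (median 9 months after relapse) | Same, median 6–18 months |
|---|---|---|---|
| 0% | about 4% | about 4% | about 4% |
| 5% | about 6.5% | about 6% | 5–7% |
| 10% | about 11% | about 8% | 6.5–11% |
| 15% | about 16% | about 11% | 8.5–17.5% |

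The time from relapse to death is also an assumption.

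**4. Second setting.** Here 15% of DFS events are deaths without relapse, accrual is 3.5 per month and follow-up is capped at 2 years per patient.

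- At 5% and 10% missed, type I error is 6.0% and 9.2% with censoring at therapy start, and 5.5% and 7.3% with deaths counted.
- A true 2-year DFS of 33% is estimated as 34.6% and 36.3%, or 34.1% and 35.2%, respectively.
- A true 53% with 10% missed is estimated as 55.9% or 54.7%.

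The bias is upward in every case.

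**The case against.** **Suspected relapse is to be worked up.** Section 7.5.7 waives imaging only when relapse is not suspected. Section 7.5.8 has any concern trigger imaging or biopsy, and 7.7.4 asks for every effort to confirm. The DFS definition requires first evidence, not confirmation; the word confirmed in 7.7.5 governs the move between follow-up phases. Many such relapses would therefore be recorded before other therapy starts. This stands, and it means the number affected may be small.

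**Data may continue anyway.** A reader might infer that a relapse after new therapy is never recorded. The documents do not support that: 7.5.8 and 7.7.4 continue relapse follow-up for 2 years. The fault is a contradiction between sections.

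**Censoring at therapy start.** A reader might infer that these patients are censored on that date. No section says so; read literally, the end-of-study rule would keep them at risk.

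**Error rates of 20–33%.** Carrying patients as disease-free to study end with no later death counted would give 9.5%, 20% and 33% at 5%, 10% and 15% missed. That does not fit 7.7.5, which keeps survival contact until death, and death is a DFS event. One reservation: 4.5 and footnote q tie survival calls only to documented progression, so the text is not uniform here either.

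**Section 5.6.4.2.** A reader might infer that anyone given other cancer therapy leaves the trial entirely. The prohibition covers only screening and treatment, and the same section states that nothing is prohibited in post-treatment follow-up. The removal wording is unclear; it does not prove that DFS follow-up is lost.

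**Conclusion.** The point holds as a contradiction in follow-up rules for the primary endpoint, together with a missing analysis rule for a foreseeable event. Where the stop rule is followed, relapse after therapy started without documented relapse is missed unless the patient later dies, and DFS is overstated against the 33% null.

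The size depends on a share that the documents do not give. At an assumed 10% of relapses missed, type I error is about 11% with censoring at therapy start, or about 8% with later deaths counted (6.5–11% for a median of 6–18 months from relapse to death), against about 4% with none missed. The 2-year estimate is about 1–3 points too high at 5–10% missed. These figures also assume exponential DFS and 35 patients. They show sensitivity and do not predict how many relapses will be missed. The change should be made, because relapse dates not collected at the time may be unrecoverable.

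**What to change.** - Reconcile 4.5, footnote q, 7.4.3 and 7.7.5 with 7.5.8 and 7.7.4, so that relapse status and dates of new therapy are collected at the existing 12-weekly contacts after new therapy, until relapse, death or study end.
- In 5.6.4.2, clarify that patients removed under that rule remain in DFS and OS follow-up. The treatment rule itself stays as it is.
- In section 9, state how new anti-cancer therapy before documented relapse is handled in the primary DFS analysis.
- Add a sensitivity analysis that counts the start of such therapy as a DFS event on that date.

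The cost is one or two extra questions at contacts already scheduled, plus protocol and SAP wording. Reported DFS may be slightly lower. With complete capture, type I error returns to about 4%.
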